Medical assessments include a complete neurologic examination including documentation of cranial nerve, motor, sensory, cerebellar, and deep tendon reflex examinations; interim history (since last visit); vital signs; physical examination (at baseline); targeted physical exam (Day 0-28, End of Radiation +2-+110 weeks, and Post-treatment follow up visits) and ECOG performance status. To be performed within 3 days prior of each dose of vaccine. Repeat medical assessment is not required at baseline if history and physical has been performed within 3 days of vaccine administration on day 0.

Serum HIV antibody should be completed within 6 months of initiating treatment.

Serum hepatitis B & C antibody should be completed within 6 months of initiating treatment.

Chemistry panel: Na+, K+, Cl, CO2, glucose, (BUN), creatinine, albumin, alkaline phosphatase, ALT, AST, total bilirubin, thyroid stimulating hormone (TSH), calcium, and ANA to be performed within 16 days prior to screening/ baseline per protocol. TSH is optional after screening visit.

In females of child-bearing potential, Beta-HCG to be done at baseline 48 hours prior to treatment and within 48 hours of any dose of vaccine or radiation.

CT chest, abdomen, and pelvis and MRI (if target lesion is best visualized by MRI)

Correlative biomarker studies (blood): 6 (10 mL) green top sodium heparin tubes for PBMC; 1 (8.5 mL) SST tubes for serum samples.

Radiotherapy schedule and dose selected by treating radiation oncologist. Radiotherapy will begin at least 2 weeks and ideally not more than 4 weeks after first administration of FPV-Brachyury (Dose 3).

 RECIST based assessment includes using RECIST principles (see [Section 10.5](#)) to measure the “target” lesions, defined as those meeting RECIST requirements for measurability and those that will be treated with radiation as defined by minimum requirements of the protocol. “Non-target” lesions may include those that are not measurable by RECIST or those that are measurable and not treated with radiotherapy at the dose required by protocol (per [Section 6.3.1](#)).

Time noted is from end of radiation or until resolution of AEs related to radiation, whichever is later

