### 4.2 Description of Trial Procedure

Patients will be treated with 2 priming doses of MVA-BN-Brachyury (Doses 1 and 2) and 1 dose of FPV-Brachyury (Dose 3) prior to initiation of radiotherapy. MVA-BN-Brachyury will be administered on Day 0 and approximately Day 14 (+ / - 2 days) followed by FPV-Brachyury on approximately Day 28 (+ / - 2 days). Radiotherapy will begin at least 2 weeks and not more than 4 weeks after first administration of FPV-Brachyury (Dose 3). Radiotherapy will proceed according to the dose and schedule selected by the treating radiation oncologist with guidelines detailed in [Section 6.3.1.2](#). The trial team must collect documentation of the dose and schedule of radiotherapy administered. The dose and schedule must comply with radiotherapy minimum requirements as defined in [Section 6.3.1](#).

At least 2 weeks following completion of radiotherapy (or upon resolution of any reversible AEs related to radiotherapy to Grade 1 or baseline if ongoing beyond 2 weeks), the patient will resume vaccination with FPV-Brachyury (Dose 4) and proceed to ongoing booster doses with FPV-Brachyury at 4-week intervals until 4 booster doses with FPV-Brachyury have been administered (Doses 4, 5, 6, 7). Subsequent vaccine doses will be administered in 12-week intervals through

approximately 2 years beyond completion of radiotherapy (Doses 8, 9, 10, 11, 12, 13). A final visit will occur 30 days after the last treatment visit.

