Modified Response Evaluation Criteria in Solid Tumors (mRECIST): Standard Response Evaluation Criteria in Solid Tumors (RECIST) Version 1.1 to be used only for radiographic assessment of the irradiated tumor(s) (target lesions). Non-irradiated tumors (non-target lesions) will not be part of the mRECIST assessment. Refer to Section 3.5.3.2 for additional details.

**Response:** Response for the primary analysis will be determined using mRECIST or Immune-Related Response Criteria (irRC), in which only target tumors receiving adequate radiotherapy will be considered for RECIST assessment and primary endpoint analysis. Progression of non-

BRACHY-CHOR-001

target lesions will be assessed as exploratory analyses based on standard RECIST 1.1 for this trial. Refer to Section 3.5.3.2 for additional details.

**Progressive Disease (PD)**: Advancement of disease as defined by target tumor enlargement from nadir using mRECIST or irRC. Progression of non-target lesions will not be considered as disease progression for the primary endpoint analysis of this trial.

**Target Lesions:** Only tumors that are measurable and have received adequate radiotherapy will be considered target lesions for determination of response. All other tumors will be considered non-target lesions.

**Objective Response (OR)**: A subject achieving Complete Response (CR) or Partial Response (PR) per mRECIST or irRC.

Objective Response Rate (ORR): The proportion of subjects meeting the criteria for OR.

**Duration of Response**: From the time that criteria are first met for CR or PR (whichever is first recorded) until the first date that recurrent or progressive disease is objectively documented. The smallest target-tumor measurements on trial (i.e., nadir tumor load) will be used as reference for progressive disease.

**Progression Free Survival (PFS)**: The time interval from the date of first trial vaccination to objective tumor progression, or death from any cause occurring prior to tumor progression. The rate of PFS at a fixed time point is defined as the proportion of subjects who have not experienced objective progression or death from the date of first trial vaccination to the fixed time point of interest.

**Brief Pain Inventory-Short Form (BPI-SF)**: A questionnaire to evaluate the severity of a subject's pain and the impact of this pain on the subject's daily functioning.

02 November, 2021

BRACHY-CHOR-001

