#### 1 Trial Overview

## 1.1 Trial Description

This is a single-arm phase 2 clinical trial using a Simon two-stage optimal design (Simon, 1989). The goal is to demonstrate that BN-Brachyury plus radiation therapy can induce objective radiographic responses in subjects. In stage 1, a minimum threshold of activity will be needed to proceed to stage 2.

[figure not shown]
Stage 1: Enroll 10 subjects. If objective response (OR) is not achieved in any subjects, the trial will be stopped for lack of activity. If OR is achieved in ≥1 subject, the trial will proceed to stage 2. If any subject is not evaluable for the primary endpoint, the subject may be replaced.

Stage 2: Enroll an additional 19 subjects for a total of 29 subjects. If any subject is not evaluable for the primary endpoint, replacement subjects may be enrolled until a total of 29 subjects are evaluable for the primary endpoint.

Subjects will be treated with two priming doses of MVA-BN-Brachyury (Doses 1 and 2) and one dose of FPV-Brachyury (Dose 3) prior to initiation of radiotherapy. Radiotherapy will begin at least 2 weeks and not more than 4 weeks after first administration of FPV-Brachyury (Dose 3). At least 2 weeks following completion of radiotherapy (or upon resolution of any reversible AEs related to radiotherapy), the subject will resume vaccination with FPV-Brachyury and proceed to ongoing booster doses with FPV-Brachyury through approximately 2 years beyond completion of radiotherapy. A final visit will occur 30 days after the last treatment visit. Refer to Figure 1 for a summary of the trial vaccine schedule.

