#### 3.5.3.3.1 Additional Analyses of the Primary Efficacy Endpoint

Baseline tumor measurements will be taken during the screening period. Objective tumor responses will be assessed every 3 months starting approximately 14 weeks after radiation therapy. Besides ORR based on the best post-treatment tumor assessment within 12 months after radiation therapy and during the trial, ORR will also be summarized for the EAS by visits with scheduled tumor assessments.

Best post-treatment tumor responses within 12 months after radiation therapy and during the trial by mRECIST will also be summarized for the EAS by location of primary tumor and histologic subtype (refer to subgroups summarized in Section 3.3), and for the FAS as a sensitivity analysis. For sensitivity analyses based on the FAS, subjects without post-treatment tumor assessments will be analyzed as non-responders (regardless of survival status) for OR endpoints.

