## 3.5.3.4 Secondary Efficacy Analyses

## 3.5.3.4.1 PFS Based on Target Lesion(s)

PFS is defined as the time interval from first vaccination to objective tumor progression based on the mRECIST criteria or death, whichever occurs first. Subjects who do not have disease progression or have not died will be censored at the date when the last tumor assessment determines a lack of target tumor progression. The product-limit Kaplan-Meier curve will summarize PFS graphically. Median survival and 95% confidence intervals will be computed based on the product limit method (Greenwood's formula for the standard error estimate) overall and by subgroups defined in Section 3.3. Progression-free survival rates will be summarized by visit where scheduled tumor assessment is performed, along with their Wilson score confidence intervals.

Primary analyses of PFS will be based on the EAS. PFS rates will also be summarized for the FAS where subjects without post-treatment tumor assessment will be considered to have progressed. Median survival and 95% confidence interval will not be analyzed for the FAS, as these estimates will not differ from those for the EAS because censoring at time 0 is equivalent to excluding these subjects.

Additionally, PFS from current treatment versus PFS from previous treatment will be explored. The ratio of current treatment PFS in days / previous treatment PFS in days for each subject will be calculated. Summary statistics will be presented for EAS. It will also be summarized for EAS by current radiation treatment dose categories: <= median current radiation dose in Gray and > median current radiation dose in Gray. Highest dose of radiation treatment for each subject is used as defining the current radiation treatment dose categories. Subject's most recent previous treatment will be used for the derivation and calculation of PFS from previous treatment. Figures will also be generated to present the ratio by overall and by current treatment radiation dose categories.

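### By-visit PFS rates are tied to end of radiation, but PFS is counted from first vaccination, so a by-visit rate is not the fixed-time rate that the SAP defines

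*SAP*

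**What the plan says.** **PFS clock.** SAP 3.5.3.4.1 states: "PFS is defined as the time interval from first vaccination to objective tumor progression based on the mRECIST criteria or death, whichever occurs first". The SAP's General Definitions add: "The rate of PFS at a fixed time point is defined as the proportion of subjects who have not experienced objective progression or death", counted "from the date of first trial vaccination to the fixed time point of interest".

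**Reporting of rates.** SAP 3.5.3.4.1 then says: "Progression-free survival rates will be summarized by visit where scheduled tumor assessment is performed, along with their Wilson score confidence intervals". Protocol 10.4.5.2 plans the same by-visit rates with Wilson intervals.

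**Visit clock.** SAP 3.5.3.3.1 says: "Objective tumor responses will be assessed every 3 months starting approximately 14 weeks after radiation therapy". In the trial procedure schedule (Protocol 1.5, SAP Appendix 1), every post-baseline scan visit except the 30-day follow-up is labelled End Radiation plus a number of weeks: 14, 26, 38 and so on to 110. Footnote 11 adds: "Time noted is from end of radiation or until resolution of AEs related to radiation, whichever is later".

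**Which set gets what.** For the EAS, SAP 3.5.3.4.1 plans a Kaplan-Meier curve, the median with a 95% interval, and the by-visit rates. For the FAS it plans only the rates, with subjects lacking a post-treatment tumor assessment counted as progressed. It omits the FAS median on the ground that censoring those subjects at time 0 amounts to leaving them out.

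**The concern.** A visit label is not a fixed time on the PFS scale. The time from first vaccination to a given scan visit depends on when radiation starts, how long the course lasts and, if footnote 11 applies to scans, how long radiation AEs persist. Neither document maps visits to weeks since first vaccination or names fixed times for the PFS rates.

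Three things are at stake:

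- The by-visit figures do not meet the SAP's own definition of a PFS rate, yet would be reported under that name.
- They are the whole PFS result for the FAS. That set includes anyone given any vaccine dose, so a subject who stops before radiation belongs to it but has no End Radiation anchor. The rule for missing post-treatment assessments covers such a subject only if there is no later scan, and a scan is scheduled at the 30-day follow-up.
- The trial is single-arm. Protocol Table 1 gives its PFS background figures in calendar time (for example, 73.0% at 9 months), and a by-visit proportion cannot be set beside them.

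**Working it through.** **Inputs from the documents**

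- Dose 3 on Day 28 (Protocol 4.2). Radiation starts 2 to 4 weeks later (Protocol 4.2, SAP 1.1), so nominally Day 42 to Day 56. Footnote 9 of the schedule gives the 4-week limit only as an ideal.
- Shortest course named: 1 fraction (Protocol 6.3.1.1).
- Longest course described: 50.4 Gy plus up to 27 Gy at 1.8 Gy per fraction (Protocol 6.3.1.2). If all of it is given at 1.8 Gy, that is 77.4 / 1.8 = 43 fractions.
- Schedule column for radiation: Day 42-70, marked approximate.

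**Assumptions not in the documents**

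- 5 fractions per week, with 4 to 7 as a range.
- Exponential PFS with a median of 9 months (the order of the medians in Protocol Table 1) or 24 months (a slower alternative, because only irradiated lesions count here).

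**Check on a stated figure.** No power or time-point figure is stated for PFS. The timeline can be checked against the stated trial duration of up to 29 months (Protocol 4.3). Duration = (end-of-radiation day + 110 x 7 + 30) / 30.44.

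- End on Day 42: 842 / 30.44 = 27.7 months.
- End on Day 70: 870 / 30.44 = 28.6 months. So Day 42-70 reproduces the stated duration.
- End on Day 114 (derived below): 914 / 30.44 = 30.0 months. The longest guideline course with the latest start fits neither the Day 42-70 column nor 29 months. These passages need to be reconciled.

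**When the End Radiation + 14 weeks visit falls.** Weeks since first vaccination = end-of-radiation day / 7 + 14.

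- Earliest: 1 fraction on Day 42 gives 42/7 + 14 = 20.0 weeks.
- Schedule's upper end: Day 70 gives 70/7 + 14 = 24.0 weeks, a spread of 4.0 weeks.
- Latest: 43 fractions at 5 per week span 58 days from first to last. From Day 56 they end on Day 114, giving 114/7 + 14 = 30.3 weeks. The spread is 72 days, or 10.3 weeks: 8.3 from course length and 2.0 from the start window.
- Sensitivity: 43 fractions at 7 to 4 per week give a spread of 8.0 to 12.3 weeks. If the longest course is 20 fractions, it is 5.6 weeks.

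Visit windows, and any AE-related delay of the anchor, would add to these.

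**What that does to the rate.** PFS(t) = 0.5^(t / median), with medians of 39.1 weeks (9 months) and 104.4 weeks (24 months):

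| Median | Week 20.0 | Week 24.0 | Week 30.3 | Gap, 4 weeks | Gap, 10.3 weeks |
|---|---|---|---|---|---|
| 9 months | 70.2% | 65.4% | 58.5% | 4.8 points | 11.7 points |
| 24 months | 87.6% | 85.3% | 81.8% | 2.3 points | 5.8 points |

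These are gaps between two subjects with identical disease behaviour who share one visit label. The pooled rate would lie between the two values, at a point set by the trial's mix of radiation courses.

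**The case against.** The strongest reply is that the main PFS analysis is sound. The EAS is primary for PFS, its Kaplan-Meier curve and median run from first vaccination, and the by-visit rates are descriptive, with no test or decision rule. That stands, and it limits the point to the rates.

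A second reply is that status at a given visit after radiation is a sensible summary: it follows the scan schedule, shares the primary endpoint's anchor, and gives all subjects at a label the same number of scheduled scans. That also stands, as a reason to keep the table under an accurate label. It does not make the figure a rate at a fixed time from first vaccination.

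Third, the size is easily overstated. Ten weeks sets one extreme against the other. Protocol 2.5.10 expects radiation above the minimum in most cases, and the boost is given as an upper limit. A 9-month median comes from systemic-therapy trials assessed by RECIST, whereas PFS here ignores non-target progression. Hence the ranges above. The AE-delay element is also uncertain: Protocol 4.2.2.2 and 10.4.3 and SAP 3.6 time the first scan from completion of radiotherapy, unlike footnote 11.

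A reader might infer that the by-visit rates will bias a planned comparison between radiation regimens. The documents do not support that. The subgroups are tumor location and histology, and the radiation-dose categories apply only to the current-to-previous PFS ratio and the percent-change plots.

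Finally, fixed-time rates do not fully remove the dependence on radiation length, because progression is detected at radiation-anchored scans. At 18 months (day 548), the short-course subject was last scanned at week 68 (6 + 62), while the long-course subject's nominal scan falls on day 548 itself (114 + 62 x 7). With the 9-month median, apparent PFS would be 30% versus 25% if that scan counts. This stands as a limit of the fix.

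**Conclusion.** The inconsistency is real and lies within the SAP: rates are defined at fixed times from first vaccination but tabulated by visits counted from end of radiation. At one label, follow-up can differ by 4 weeks on the schedule's own column and by up to about 10 weeks at the extremes, the latter resting on 43 fractions at an assumed 5 per week. The matching gap is about 2 to 12 percentage points, on assumed exponential medians of 24 to 9 months.

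This concerns a secondary endpoint. The EAS Kaplan-Meier curve and median are unaffected, and so is the primary ORR, whose 12-month window starts at the end of radiation. The change is still worth making, because the by-visit rates are the only FAS result for PFS and subjects who never receive radiation have no visit anchor.

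**What to change.** - In SAP 3.5.3.4.1, report PFS rates from the Kaplan-Meier fit at prespecified times from first vaccination (for example 12, 18 and 24 months), with Greenwood-based 95% intervals, for both the EAS and the FAS.
- In the FAS fit, keep the rule that subjects without post-treatment assessment count as progressed, rather than censoring them at time 0, and state the event date assigned to them.
- State whether the rule in SAP 3.4.2, which counts early withdrawals without a recorded response as progressed in by-time-point PFS analyses, applies to the new rates.
- Keep the protocol's by-visit proportions with Wilson intervals as a supplementary table. Label it by weeks since end of radiation, not as PFS rates at a fixed time, and say how subjects who never receive radiation are shown.
- Record the change in SAP Section 4, since Protocol 10.4.5.2 specifies the by-visit rates.

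The cost is some SAP wording and one extra table, with no new data. Radiation-anchored scan timing will still affect when progression is detected, and a footnote to the new table should say so.

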##### **10.4.5.2 Secondary Efficacy Analysis**

The primary analysis population for the secondary endpoints is the evaluable analysis set. Secondary analysis will also be performed on the FAS.

PFS is defined as the time interval from first treatment of MVA-BN-Brachyury to objective tumor progression based on target lesion(s) or death whichever occurs first. Patients who do not have disease progression or have not died will be censored at the date when the last tumor assessment determines a lack of progression. The product-limit Kaplan-Meier curve will summarize PFS graphically. Median survival and their 95% confidence intervals will be computed. Progression-free rates will be summarized by visit where scheduled tumor assessment is performed, along with their Wilson score confidence intervals.

PFS per modified RECIST 1.1 based on the investigator's assessment will be used as one of the two secondary efficacy endpoints. The immune-related radiographic response modification requires a confirmation of progressive disease (PD) at least 4 weeks later with imaging; once confirmed, the date of progression is defined as the first date that the total tumor burden was shown to have increased by at least 20% compared with the nadir.

The BPI-SF will be scored as follows:

- Pain intensity Worst, Least, Average in the last week and pain intensity Right now as recorded in eCRF.
- Composite pain severity score (a mean severity score of the above four pain items)
- Composite pain interference score (a mean of the seven interference items). This will be calculated if at least four of the seven interference items have been completed on a given administration. Otherwise, the pain interference score will be considered missing.

Summaries for BPI-SF will be provided by study period and include continuous summary statistics.

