**BRACHY-CHOR-001** 

- Completed radiation therapy, and
- At least 3 out of 4 booster doses of FPV-Brachyury in 14 weeks after radiation, and
- Have both baseline (defined as measurement prior to first prime dose of MVA-BN-Brachyury), and at least one post-baseline computed tomography (CT) or magnetic resonance imaging (MRI) scan for objective tumor evaluation.

The primary analysis population for ORR anytime within 12 months after completion of radiation and secondary efficacy endpoints is the EAS. Subjects who failed to meet the evaluable criteria will be replaced to retain the statistical power unless four or more responses have been observed or the number of responders will still be less than four even if all replacement subjects would be responders. If there are more than 10 evaluable subjects at the end of stage 1 analysis or more than 29 evaluable subjects at the end of stage 2 analysis, primary evaluation will be based on the first 10 accrued or first 29 accrued evaluable subjects. Sensitivity analyses will include all evaluable subjects if applicable.

The FAS consists of all subjects who have enrolled and received any dose of MVA-BN-Brachyury or FPV-Brachyury. This is the primary analysis set for safety and immune response, and the secondary analysis set for efficacy.

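### PFS is timed from first vaccination but analysed mainly in a set that patients enter months later, so the curve and median carry guaranteed survival time and have no FAS counterpart

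*SAP*

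**What the plan says.** Time origin. SAP 3.5.3.4.1: "PFS is defined as the time interval from first vaccination to objective tumor progression based on the mRECIST criteria or death, whichever occurs first". Protocol 10.4.5.2 uses the same origin: "PFS is defined as the time interval from first treatment of MVA-BN-Brachyury to objective tumor progression based on target lesion(s) or death".

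Population. SAP 3.5.3.4.1: "Primary analyses of PFS will be based on the EAS". Protocol 10.4.1 and 10.4.5.2 also make the evaluable set primary for the secondary endpoints, but 10.4.5.2 adds that a secondary analysis will be done on the FAS.

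Entry to the EAS (SAP 3.2). Two prime doses, one booster before radiation, completed radiation, "At least 3 out of 4 booster doses of FPV-Brachyury in 14 weeks after radiation", and a baseline scan plus "at least one post-baseline computed tomography (CT) or magnetic resonance imaging (MRI) scan for objective tumor evaluation". The post-baseline scan need not be free of progression.

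FAS results for PFS. SAP 3.5.3.4.1 plans by-visit rates in the FAS, counting patients with no post-treatment tumour assessment as progressed. It declines a FAS median and confidence interval, on the ground that excluding these patients is the same as censoring them at time 0. The ratio of current to previous PFS is summarised for the EAS only.

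**The concern.** Membership of the analysis set is decided by what happens after the clock starts. A patient who dies before the third post-radiation booster cannot be in the EAS, yet every EAS patient is counted at risk from the first vaccination. Protocol 4.2.5 withdraws patients from vaccination for target-lesion progression, so early clinical progressors tend to miss the three-booster requirement as well. This is guarantee-time (immortal-time) bias. At stake is the main reading of a secondary efficacy endpoint: the Kaplan-Meier curve, the median and the PFS ratio would describe patients who completed several months of treatment while appearing to describe patients from their first dose.

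**Working it through.** **1. The plan's own timeline figure.** The documents give no PFS target, event count or guaranteed time. The stated figure that tests the schedule is the duration of up to 29 months per patient (Protocol 4.3). With radiation ending on Day 70 (the schedule's Day 42-70 column), the last dose at +110 weeks and the final visit 30 days later: 70 + 770 + 30 = 870 days = 28.6 months. This agrees. Twenty-nine months allows radiation to end by about Day 83.

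**2. Guaranteed survival to the third booster.** Inputs: Dose 3 on Day 28; radiation starts 2 to 4 weeks later, so Day 42 to 56 (Protocol 4.2); boosters at end of radiation +2, +6, +10 and +14 weeks (SAP 3.5.7). The third booster falls at +10 weeks (70 days), or at +14 weeks (98 days) if one is missed. Five fractions per week is assumed.

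| Radiation course | End of radiation | Third booster | Weeks |
|---|---|---|---|
| 1 fraction, start Day 42 | Day 42 | 42 + 70 = 112 | 16.0 |
| 20 fractions, start Day 56, one booster missed | Day 81 | 81 + 98 = 179 | 25.6 |
| End on Day 83 (29-month limit), one missed | Day 83 | 83 + 98 = 181 | 25.9 |
| 43 fractions, start Day 42 | Day 100 | 100 + 70 = 170 | 24.3 |
| 43 fractions, start Day 56 | Day 114 | 114 + 70 = 184 | 26.3 |
| 43 fractions, start Day 56, one missed | Day 114 | 114 + 98 = 212 | 30.3 |

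The 43 fractions come from Protocol 6.3.1.2: 50.4 + 27 = 77.4 Gy, and 77.4 / 1.8 = 43, assuming 1.8 Gy throughout. They take 58 days. Visit windows lower the minimum to 15.1 weeks. The interval lengthens if vaccination waits for radiation adverse events to resolve.

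**3. Where the scan schedule acts.** The first scheduled post-baseline scan is at end of radiation +14 weeks: at the earliest 42 + 98 = Day 140, week 20.0. Unless an unscheduled scan is done, radiographic progression before then is dated to that scan in either analysis set. That part of a flat early curve is not due to the EAS.

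**4. Size, as an illustration only.** Assume exponential PFS with median m. Let t0 be the qualifying time and f the share of events before t0 that remove the patient from the EAS. Beyond t0, S_EAS(t) = S(t) / [1 − f(1 − S(t0))], so the EAS median is m × {1 − log2[1 − f(1 − S(t0))]}. Take m = 9 months (Protocol Table 1 medians are 8 to 9.9 months) and t0 = 3.7 to 6.0 months (Day 112 to Day 184). Then S(t0) = 0.752 to 0.630.

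| f | EAS median, months |
|---|---|
| 0 | 9.0 |
| 0.10 | 9.3 to 9.5 |
| 0.25 | 9.8 to 10.3 |
| 0.50 | 10.7 to 11.7 |
| 1 | 12.7 to 15.0 |

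At f = 1 the excess equals t0 itself, so it would be about 7 months for the 212-day case. The same formula for a rate, with m = 39 weeks: at week 44 with t0 = 16 weeks, 46% in all treated against 49%, 52% and 61% in the EAS for f = 0.25, 0.5 and 1. At week 50 with t0 = 26 weeks, 41% against 45%, 50% and 65%.

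**5. The time-0 argument.** Censoring at time 0 matches exclusion only for a patient with no usable follow-up. Two kinds of patient excluded from the EAS do not fit:
- A patient who dies before any scan has an event under the SAP's own definition, and SAP 3.4.2 censors only patients with no date of death and no progression. With 29 EAS patients and one such death, the FAS curve has fallen to 29/30 = 96.7% where the EAS curve, with no other event by then, still stands at 100%.
- A patient with a scan but fewer than three boosters has observed follow-up, possibly including progression.

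**The case against.** Four points can be made against this.

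First, a reader might infer that 16 to 26 weeks of event-free time are built in and the curve is forced flat at 1.0. The documents do not support that. The qualifying scan may itself show progression, and Protocol 4.2.5 lets a patient stay on trial after initial target-lesion progression until a confirmatory scan. Confirmed progression is dated back to the first scan showing it (Protocol 10.4.5.2). Only survival is guaranteed; progression is selected against, not excluded. Nor is 26 weeks a ceiling.

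Second, the 9-month median comes from systemic-therapy series. Here only irradiated target lesions count, and rapidly progressing multi-site disease is excluded, so early events may be fewer. With an assumed 24-month median and f = 0.5, the formula gives 25.8 to 26.9 months, about 7% to 12% upward against 19% to 30% at 9 months. This stands, and it is why no single figure should be quoted.

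Third, safeguards are planned for the rates. FAS by-visit rates count unscanned patients as progressed, and SAP 3.4.2 counts early withdrawals without a response as progressed in the by-time-point analyses. These partly offset the bias for rates, but they do nothing for the curve, the median or the ratio.

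Fourth, PFS is descriptive in a single-arm trial and success rests on ORR alone (SAP 3.5.3.3). That limits the consequence but does not make the median interpretable from first vaccination.

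**Conclusion.** The point holds for the EAS Kaplan-Meier curve, median and PFS ratio. Each carries guaranteed survival of at least about 16 weeks, and up to about 26 to 30 weeks under the longer schedules, together with selection against early clinical progressors. The direction is upward.

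The size cannot be derived from the documents. It is zero if there are no early deaths, clinical progressions or withdrawals. Under an exponential 9-month median it reaches about 4 to 6 months only in the extreme where every early event removes the patient. It would be wrong to read those figures as the expected inflation: neither f nor the median is given for this trial.

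The firmer finding is the missing counterpart. The SAP's reason for having no FAS median is incorrect for two identifiable groups. The omission departs from the FAS analysis planned in Protocol 10.4.5.2 and is not listed in SAP Section 4. No test or success rule is affected, so this is a correction that should be made to a secondary endpoint, not a threat to the primary conclusion.

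**What to change.** In SAP 3.5.3.4.1:

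- Delete the sentence declining the FAS median and its time-0 argument.
- Make the Kaplan-Meier curve, median and 95% confidence interval from first vaccination in the FAS the main PFS result. Count deaths before any scan as events, use all available scans, and censor at time 0 only patients alive with no post-baseline scan. Use the counted-as-progressed rule for unscanned patients as a sensitivity analysis.
- Keep EAS PFS as supportive, labelled as conditional on completing the qualifying treatment and scan. Delayed entry at the third booster alone would not be enough, because it ignores the scan requirement, which on schedule is met later.
- Show the current/previous PFS ratio for the FAS as well.
- Record the change of main population in SAP Section 4, since Protocol 10.4.1 and 10.4.5.2 name the evaluable set as primary for secondary endpoints.

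The cost is SAP wording and a little programming on data already collected, and possibly a less favourable PFS figure.
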